# 4.3. Secondary Endpoint(s) Analyses

### 4.3.1. Key secondary endpoint(s)

### 4.3.1.1. Definition of endpoint(s)

The following PK parameters will be determined if data permit:

- Cmax, Cmin, and Tmax
- Area under the plasma concentration-time curve (AUC(0-t), AUC(0-τ), [repeat dosing]])
- Apparent terminal phase elimination rate constant  $(\lambda z)$  (single dose)
- Apparent terminal phase half-life (t1/2) (single dose)
- Systemic clearance of parent drug (CL)
- Volume of distribution (V)
- Other parameters and analyses as appropriate and data permits, such as dose proportionality and time-invariance.

#### 4.3.1.2. PK Evaluation

Pharmacokinetic parameters for GSK3745417 administered IV in this study will be calculated by standard non-compartmental analysis according to current working practices and using the currently supported version of Phoenix WinNonlin.

Analysis procedures will follow GSK VQD-REF-015788 unless otherwise noted below. All calculations of non-compartmental parameters will be based on actual sampling times. PK analysis of GSK3745417 will be the responsibility of the Clinical Pharmacology Modeling and Simulation (CPMS) Department, GSK. PK analysis of GSK3745417 drug concentration-time data will be conducted by noncompartmental methods under the direction of CPMS, GSK.

Statistical analyses of the PK parameters data will be the responsibility of Clinical Statistics, GSK. All PK analyses will be performed on the PK Analysis Set.

Drug concentration-time data will be listed for each participant and summarized by descriptive statistics at each time point by dose. PK parameter data will be listed for each participant and summarized by descriptive statistics by dose and visit.

All derived PK parameters will be summarised using descriptive statistics, graphically presented (where appropriate) and listed. For each of these parameters, except Tmax, the following summary statistics will be calculated for each dose level and treatment day: median, minimum, maximum, arithmetic mean, 95% CI for the arithmetic mean, std, coefficient of variation (%CV =  $100*(\text{sqrt}(\exp(\text{SD}^2) - 1)))$ ) (where SD = SD of natural log transformed data), geometric mean, 95% confidence interval for the geometric mean and std of natural logarithmically transformed data. For Tmax, median, maximum, minimum, arithmetic mean, 95% CI, and std will be calculated. The first point, last point

and number of points used in the determination of  $\lambda z$  will be included on the listing of the derived parameters.

All PK parameters will be reported to at least 3 significant digits, but to no more significant digits than the precision of the original data.

The data from this study may be combined with the data from other studies for a population PK analysis and/or exposure-response analysis, which will be reported separately.

The following PK statistical analyses will only be performed if sufficient data are available (i.e., if participants have well defined serum profiles). Analyses may not be performed on Cmax or AUC if the team considers there are a large amount of data either below the limit of quantification or non-calculable; alternatively, if the dose with limited data is at the lower end of the dose range, the data of this dose will be excluded, and the appropriate analysis conducted on the rest of the data. However, if there are non-calculable PK parameter data at intermittent doses no statistical analyses will be performed. A minimum of 3 doses will be required to assess dose proportionality.

Dose proportionality of GSK3745417 will be assessed by visual inspection of:

- Scatter plots (+geometric mean and 95% confidence intervals, as appropriate) of GSK3745417 dose-normalized PK parameter vs dose will be produced for [or AUC(0-t) and Cmax.
- Scatter plots of GSK3745417 log10 PK parameter vs log10 dose will be produced for AUC(0-t) and Cmax.

The PK parameters will be dose-normalized by the actual dose that each patient received (i.e., Cmax/actual dose).

Other PK figures may be produced if deemed appropriate.

# 4.3.2. Supportive secondary endpoint(s)

The list of terms for adverse events of special interest (AESI) is in Appendix 4 of the protocol and includes events that may be immune-related or related to cytokine release syndrome (CRS) or tumor lysis syndrome (TLS). AESIs and the type of event will be recorded in the CRF.

The list of AESIs is provided below and may be updated at the time of database lock based on the MedDRA version in use at the time of reporting and/or any additional safety information available from GSK that may determine a need to consider additional events of interest.

### Cytokine-related AEs

Cardiopulmonary or hemodynamic toxicity starting within 24 hours of study treatment that requires >40% FiO2, vasopressor administration, antiarrhythmic agent, or other significant medical intervention. Asystole, as measured by ECG, or bradycardia that is symptomatic and requires medical intervention. Some of the MedDRA preferred terms relevant to cytokine-related AEs include cytokine release syndrome, cytokine storm, cytokine increased and systemic inflammatory response syndrome.

### Immune-related AEs

[figure not shown]
Pneumonitis (reported as AESI if $\geq$ Grade 2)					
Acute interstitial		D.,			
pneumonitis	Interstitial lung disease	Pneumonitis			
Colitis (reported as AESI if ≥ 0	Grade 2 or any grade resultir	ng in dose modification or			
use of systemic steroids to trea	t the AE)				
Intestinal Obstruction	Colitis	Colitis microscopic			
Enterocolitis	Enterocolitis	Gastrointestinal			
Enterocontis	hemorrhagic	perforation			
Necrotizing colitis	Diarrhea				
Endocrine (reported as AESI is		d resulting in dose			
modification or use of systemic	T				
Adrenal Insufficiency	Hyperthyroidism	Hypophysitis			
Hypopituitarism	Hypothyroidism	Thyroid disorder			
Thyroiditis	Hyperglycemia, if ≥Grade				
	ketosis or metabolic acidos	sis (DKA)			
Endocrine (reported as AESI)					
Type 1 diabetes mellitus (if					
new onset)					
Hematologic (reported as AESI if $\geq$ Grade 3 or any grade resulting in dose					
modification or use of systemic	c steroids to treat the AE)				
Autoimmune hemolytic	A 1	Thrombotic			
anemia	Aplastic anemia	Thrombocytopenic (TTP)			
Idianathia (an immuuna)	Disseminated	Purpura (TTP)			
Idiopathic (or immune)	Intravascular	Hemolytic Uremic			
Thrombocytopenia Purpura (ITP)	Coagulation (DIC)	Syndrome (HUS)			
Any Grade 4 anemia regardles					
		ting in dose modification			
Hepatic (reported as AESI if $\geq$ Grade 2, or any grade resulting in dose modification or use of systemic steroids to treat the AE)					
Transaminase elevations					
Hepatitis	Autoimmune hepatitis	(ALT and/or AST)			
Infusion Reactions (reported as	s AESI for any grade)	[ [ [ [ [ [ [ [ [ [ [ [ [ [ [ [ [ [ [			
Allergic reaction	Anaphylaxis	CRS			
Serum sickness	Infusion reactions	Infusion-like reactions			

Neurologic (reported as AESI for any grade)				
Autoimmune neuropathy	Guillain-Barré syndrome	Demyelinating polyneuropathy		
Myasthenic syndrome				
Ocular (report as AESI if $\geq$ G	rade 2 or any grade resulting	in dose modification or		
use of systemic steroids to trea	it the AE)			
Uveitis	Iritis			
Renal (reported as AESI if $\geq$ 0	Grade 2)			
Nephritis	Nephritis autoimmune	Renal Failure		
Renal failure acute	Creatinine elevations (report as AESI if ≥Grade 3 or any grade resulting in dose modification or use of systemic steroids to treat the AE)			
Skin (reported as AESI for any grade)				
Dermatitis exfoliative	Erythema multiforme	Stevens-Johnson syndrome		
Toxic epidermal necrolysis				
Skin (reported as AESI if ≥ Gr	rade 3)			
Pruritus	Rash	Rash generalized		
Rash maculo-papular				
Any rash considered clinically significant in the physician's judgment				
Other (reported as AESI for any grade)				
Myocarditis	Pancreatitis	Pericarditis		
Any other Grade 3 event which	h is considered immune-rela	ted by the physician		

Summaries of the number and percentage of subjects with treatment-emergent AESIs will be provided for each type of event separately by PT and maximum grade. A summary of the number of participant and occurrences of treatment-emergent cytokine release syndrome adverse events and infusion related reactions will be produced. These summaries will be based on data as recorded in the eCRF.

# 4.4. Exploratory Endpoint(s) Analyses

# 4.5. Other Safety Analyses

The safety analyses will be based on the Safety Analysis Set, unless otherwise specified.

### 4.5.1. Extent of Exposure

Exposure to GSK3745417 will be summarized according to cumulative actual dose, number of cycles, time on study treatment (weeks) with separate sections for induction dosing and maintenance dosing in one table. Descriptive statistics including mean, median, standard deviation, minimum, and maximum will be calculated.

The cumulative dose, converted to and displayed in mg, is the sum of the actual dose administered in micrograms during each infusion for a subject throughout the study. For induction dosing, cumulative dose will be summarized by cycle. For induction cycles, the number of cycles will be calculated by the number of GSK3745417 doses received during the induction phase divided by 10. For subsequent maintenance cycles, the number cycles will be calculated by (last maintenance infusion date – first maintenance infusion date + 7)/28.

Subject level details for extent of exposure to study treatment will be listed. The listing will include cycle, total dose taken per cycle, cycle day, start and stop dates, scheduled dose, actual dose, and cumulative dose. Exposure data will be listed in both units (mg and  $\mu$ g).

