# CONFIDENTIAL

DE Cohort	Screeningª	Cycle (Induction Period)			Follov (post-fin adminis	w-Up al dose stered)	
Study Procedure		Intervent (In-P	tion Period atient)	Observation Period (Outpatient)	TDV⁵	Follow- Up	Notes
Week	≤4	1	- 2	3 - 4	+4		
Day	≤28	-1	1 - 13	14 - 28	+30d		
Urinalysis⁰	x		Х		Х		Sample collection times: Days 1, 8 and 13 of each cycle. If urinalysis is abnormal, a microscopy should be performed.
Coagulation	x		х				Sample collection times: at screening and prior to administration of first dose of GSK3745417 and at Day 8 of each cycle. Additional coagulation samples should be collected in the event of CRS (see Section 6.4.1.4)
Study Intervention	•						· · ·
Administer GSK3745417			X				GSK3745417 will be administered the same dose within each cycle on Days 1 – 5 and Days 8 - 12 QD. Participants will receive up to 3 cycles of treatment before moving to Q1W or Q3W dosing (Section 6.1). See Section 4.1 for maximum duration of study intervention. See Section 4.1 for safety and tolerability parameters to be reviewed prior to each daily dose
Non-Azole Antifungal		х	Х	Х			Non-azole antifungals should be administered if indicated, per local standard, on Day -1 through Day 28 of each cycle.
Tumor Lysis Syndrome Prophylaxis		x					All participants should receive tumor lysis syndrome (TLS) prophylaxis prior to date of first dose of each cycle on Day -1 according to institutional guidelines (e.g., participants should receive IV fluids ± allopurinol and consider alkalization of urine and

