### Intra-patient dose escalation

In Part 1, participants are permitted to dose escalate between the 2-3 induction 5/2/5 q28d cycles based on discussion and agreement with Medical Monitor and the Investigator after reviewing available safety and laboratory data, and in line with the following safety and tolerability parameters:

- Investigator and MM must both consider that dose escalation is in the best interests of the participant
- Participant must have received at least 7 of the 10 doses in the prior cycle
- Participant must not have experienced:
  - $\circ$  Any Grade  $\geq$ 3 adverse event
  - $\circ$  Grade  $\geq$ 3 TLS
  - A DLT (which includes Grade 3 CRS, all non-hematologic Grade 3 events with a few exceptions as per Table 7)
  - More than 1 episode of Grade 2 CRS in the previous cycle
  - Evidence of ongoing immune related AEs during the observation period (sustained or intermittent Grade ≥2 fever ongoing after the first week of the observation period, in which infectious cause is ruled out).

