## Holding daily dosing

Daily dosing will be continued unless there is evidence of ongoing TLS or immune activation in line with the criteria below.

Daily dosing held if:

- Ongoing Grade 3 TLS (see Appendix 11 for Cairo Bishop grading) or Grade 3 electrolyte abnormalities that are not responding to treatment
- Failure of any CRS, fevers, or chills to resolve to Grade ≤1 (with supportive treatment) within 24 hours
- Any new neurological adverse events (except for Grade ≤2 headache which responds to analgesia), until assessment and cause of neurological event is identified
- Investigator judgement that dosing should be held based on the clinical status of patient

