## 1.2. Study Design

Overview of Stu	udy Design and Key Features
Study intervention	• Part 1 will evaluate a dosing schedule of a 5 days on/2 days off schedule for 2 weeks, and then have an additional 2 weeks off dose for observation for a total of 28 days in each cycle (5 / 2 / 5 q28d). Once an MTD has been established, additional cohorts may be opened to refine dosing frequency optimization. Each cohort will include at least 3 participants. Part 1 will include intra-patient dose escalation for 3 cycles, according to safety and tolerability parameters. The starting dose for Cycle 1 will be escalated in the next dose escalation cohort until a cohort level MTD is reached.
	After 3 induction cycles, if a CR or PR (per appropriate response criteria) is observed, each patient will continue with maintenance weekly dosing at the Cycle 3 dose level until disease progression or unacceptable toxicity. Participants with progressive disease after 3 induction cycles will be withdrawn from study. Participants with stable disease or PR after 3 cycles might receive additional cycles.
Study	This is a FTIH, open-label, non-randomized study.
intervention	
Assignment	

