### 3. ANALYSIS SETS

Analysis Set	Definition / Criteria	Analyses Evaluated
Screened	All participants who were screened for eligibility.	Study     Population
Enrolled	All participants who entered the study (who received GSK3745417 or underwent a post-screening procedure). Note: Screening failures (who never passed screening even if rescreened) and participants screened but never enrolled into the study (met eligibility but not needed) are excluded as they did not enter the study.	Study     Population
Safety	All participants who take at least 1 dose of study intervention. Participants will be analysed according to the intervention they actually received.	

Study Population

Safety

Efficacy

DLT-evaluable	
 
All participants who take at least 1 dose of study intervention and are followed for the DLT observation period or are withdrawn within the DLT observation period due to meeting the DLT criteria.
 
Participants unable to receive at least 70% of scheduled doses within the DLT period for other reasons other than toxicity will not be considered evaluable
 
	Safety
PK	All participants from the Safety Analysis Set for whom a PK sample is obtained and analysed.	• PK

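### Counting induction cycles as doses received / 10 understates the cycles given whenever a dose is missed, and the result is not comparable with the maintenance cycle count in the same table

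*SAP*

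**What the plan says.** SAP 4.5.1 (Extent of Exposure) plans a table of cumulative dose, number of cycles and weeks on treatment, with separate induction and maintenance sections. For induction, "the number of cycles will be calculated by the number of GSK3745417 doses received during the induction phase divided by 10". For maintenance, the count is the days from first to last infusion, plus 7, divided by 28.

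The design defines a cycle by the calendar. SAP 1.2 describes two dosing weeks and two weeks of observation, "for a total of 28 days in each cycle". In Protocol Table 1 the drug is "administered the same dose within each cycle on Days 1 – 5 and Days 8 - 12 QD", and "Participants will receive up to 3 cycles of treatment before moving to Q1W or Q3W dosing". SAP 1.2 adds that "Participants with stable disease or PR after 3 cycles might receive additional cycles".

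Both documents foresee cycles with fewer than 10 doses:

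- Protocol 6.4.1, on holding daily dosing: "Daily dosing will be continued unless there is evidence of ongoing TLS or immune activation in line with the criteria below". Hold criteria follow, including investigator judgement.
- Protocol 4.1.2, on intra-patient escalation to the next cycle: "Participant must have received at least 7 of the 10 doses in the prior cycle". Section 6.4.1.1 repeats this.
- SAP 3, on DLT evaluability: "Participants unable to receive at least 70% of scheduled doses within the DLT period" for reasons other than toxicity are not evaluable.

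SAP 4.5.1 also summarizes cumulative induction dose by cycle. Its participant listing carries the cycle, the total dose in that cycle, dates, and scheduled and actual dose.

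**The concern.** A row labelled as number of cycles will be read as how far participants got through the planned 28-day cycles. Doses / 10 answers a different question: how many fully dosed cycles the injections would add up to. The two agree only under complete dosing, which the protocol does not assume.

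Cycle number carries meaning in Part 1. Under intra-patient escalation the dose may double in Cycle 2 and again in Cycle 3, so reaching Cycle 3 is how a participant reaches the top of the individual titration. A summary value near 2 invites the reading that participants typically stopped after two cycles, when all of them may have started a third.

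The maintenance row makes this worse. A reader comparing the two sections would take the same label to mean the same thing, but one count falls with each missed dose and the other ignores missed doses between the first and last infusion.

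**Working it through.** **Inputs.** Scheduled dosing days are 1–5 and 8–12 (Protocol Table 1). Cycle length is 28 days (SAP 1.2). The induction and maintenance rules are in SAP 4.5.1. The documents give no expected frequency of missed doses, so the dose patterns below are illustrative assumptions. The 7-of-10 pattern uses the protocol's own threshold for considering escalation; it is not a forecast of exposure.

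**Step 1: reproduce the divisor.** 5 + 5 = 10 doses per cycle. Three fully dosed cycles give 30 / 10 = 3.0. The divisor is right for complete dosing.

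**Step 2: apply the induction rule to incomplete dosing.** SAP count = total induction doses / 10. The comparison is the number of distinct cycles with at least one dose.

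| Doses in each cycle | Total | SAP count | Cycles with at least one dose | Difference |
|---|---|---|---|---|
| 10, 10, 10 | 30 | 3.0 | 3 | 0 |
| 10, 7, 10 | 27 | 2.7 | 3 | −0.3 |
| 5, 10, 10 | 25 | 2.5 | 3 | −0.5 |
| 7, 7, 7 | 21 | 2.1 | 3 | −0.9 |
| 10, 10, 1 | 21 | 2.1 | 3 | −0.9 |
| 7, 8, 7, 8 | 30 | 3.0 | 4 | −1.0 |
| 1, then stop | 1 | 0.1 | 1 | −0.9 |

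No cycle has more than 10 scheduled doses, so the SAP count can equal the number of cycles dosed or fall below it, but not exceed it. At 7 of 10 doses throughout, the shortfall is 0.9 / 3 = 30%. Different histories also coincide: 7, 7, 7 and 10, 10, 1 both give 2.1, and four cycles of 7, 8, 7 and 8 doses give the same 3.0 as three complete cycles.

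**Step 3: compare the maintenance rule.** Count = (days from first to last infusion + 7) / 28.

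- Eight weekly infusions on days 0, 7, ..., 49: (49 + 7) / 28 = 2.0.
- Four infusions on days 0, 7, 28 and 49: (49 + 7) / 28 = 2.0.

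A dose-based rule like the one for induction would use 28 / 7 = 4 weekly doses per 28 days, giving 8 / 4 = 2.0 and 4 / 4 = 1.0. Missing half the doses would therefore halve a dose-based count but leaves the planned maintenance count unchanged.

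**Step 4: what the other planned outputs show.** Doses of 5, 5, 5 and of 10, 5 both give 15 / 10 = 1.5 cycles. Cumulative dose by cycle separates them, because the first has dose in three cycles and the second in two. Weeks on treatment also separates them: with no delay between cycles, the third cycle starts on Day 2 × 28 + 1 = 57, so the first history spans about 8 to 9 weeks and the second about 5.

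**The case against.** The case for leaving the rule alone is a fair one. The SAP states its derivation openly, and a dose-equivalent count is a legitimate exposure measure. Counting every cycle with at least one dose has its own distortion, because a participant who stops after one injection scores the same for that cycle as one who received ten. The row is descriptive. DLT evaluability has its own 70% rule, and the primary endpoints (adverse events, serious adverse events, DLTs and withdrawals) do not use it. The study has been terminated and only a synoptic report of Part 1 is planned. Further display details sit in the Output and Specification document, which was not available for this review.

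Most of this stands as a limit on importance. It does not make the label correct, and it does not explain why the two sections of one table count cycles on different bases.

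Two stronger readings are tempting, and the documents do not support them. A reader might infer that the rule conceals low dosing. It does not: the same SAP section reports cumulative dose by cycle and weeks on treatment, and lists scheduled against actual dose. A reader might also infer that the shortfall falls specifically on participants with toxicity holds. The formula responds to any missed dose, including those due to acute illness, progression, withdrawal or investigator judgement. No hold frequency is given from which a safety-related bias could be sized.

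**Conclusion.** The point holds as a derivation and labelling error in one descriptive row. The induction count equals the number of 28-day cycles only if all 10 doses are given in every cycle; otherwise it is too low. The size depends on dosing patterns the documents do not predict. In the illustrations it runs from 0.3 to 1.0 cycle, and it is 0.9 of 3 when each cycle has 7 of 10 doses. The row cannot be compared with the elapsed-time maintenance row.

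No DLT, maximum tolerated dose or pharmacokinetic result changes, and the true number of cycles is recoverable from other planned outputs. It is still worth correcting, because a reported number would not be what its label says and the variable needed is already in the listing.

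**What to change.** In SAP 4.5.1, define the number of induction cycles as the count of distinct induction cycles in which at least one dose was given. Add a separate row for dose completion: doses received / doses scheduled, per cycle. That row makes visible the one drawback of the new count, that a single-dose cycle counts as one.

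Dose completion should not be called relative dose intensity. It ignores dose level, and levels can rise or be reduced between cycles: a cycle with all 10 injections at a reduced level would still show 100%. If relative dose intensity is wanted, use actual / scheduled dose amount, and state whether the scheduled amount is reset after a dose change.

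If doses / 10 is kept, label it 'full-cycle equivalents' and add a footnote that the maintenance count is based on elapsed time. The divisor should also be checked against any added cohort with a different dosing frequency, which SAP 1.2 allows for.

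The cost is one changed derivation and one extra row. No new data are needed, since cycle, scheduled dose and actual dose are already in the planned listing.

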#### 4.5.2. COVID-19

#### 4.5.2.1. COVID-19 Assessment and COVID-19 AEs

A standardized MedDRA Query (SMQ) will be used to identify all COVID-19 AEs.

